	Appendix 4 – Declaration of Helsinki	
	Appendix 5 – TGA annotated ICH GCP	

1.0 SUMMARY

This study is a prospective, randomised clinical study comparing clinical outcomes of Knee Replacement using the Oxford Knee Score (OKS), in patients receiving either Bicompartamental Knee Replacement or Total Knee Replacement performed using Stryker's robotic-arm assisted surgery system Mako, Functional and radiographic outcomes will be additionally collected as part of this study.

The study will be conducted in patients with non-inflammatory degenerative joint disease who are randomised to either the Restoris® MCK Multicompartmental Knee System for Bicompartamental Knee Replacement (BKR), or the Triathlon Total Knee System for Total Knee Replacement (TKR), with a minimum 2 year patient evaluation period.

All components used in this study are TGA approved, listed on the Australian Register of Therapeutic Goods. This study will be a phase IV post-market clinical trial.

A minimum cohort of **70** patients will be enrolled into the study in Australia.

Patients who are eligible for knee replacement surgery and meet the inclusion/exclusion criteria, will be enrolled into the study and randomised to receive either the Restoris® MCK Multicompartmental Knee System or Triathlon Primary Total Knee System. Patients will undergo a series of evaluations both pre-operatively, intra-operatively and post-operatively, in accordance with the below schedule:

PATIENT EVALUATON SCHEDULE

<http://sspintranet/sites/raqa/qms/documents/FM-CRD-029.docx>
MAKORCT-15 Final version 5.0 22 February 2018

EVALUATION	History/ Pre-Op	Intra- Op	Post op ≤5 days after surgery	6 week follow- up (± 2 weeks)	3 month follow- up (± 2 weeks)	12 month follow- up (± 1 month)	24 month follow- up (± 2 months)
Date of Visit	✓	✓	✓	✓	✓	✓	✓
Pre Op Clinical Data	✓						
Inclusion / Exclusion Criteria	✓						
Randomisation	✓						
Surgical Details (All surgery, Bicompartmental Surgery, Total Knee Replacement)		✓					
Oxford Knee Score	✓			✓	✓	✓	✓
EQ-5D	✓				✓	✓	✓
VAS Pain	✓				✓	✓	✓
New Knee Society Score	✓				✓		✓
Forgotten Joint Score	✓				✓	✓	✓
Length of Stay				✓			
MAKO CT or MAKO CT Arthrogram	✓**						
Anteroposterior (A/P) and Lateral Knee Radiographs	✓		✓*		✓	✓	✓
Skyline Knee radiographs	✓					✓	✓
Adverse Events		✓	✓	✓	✓	✓	✓
Serious Adverse Events	✓	✓	✓	✓	✓	✓	✓
Protocol Deviations	✓	✓	✓	✓	✓	✓	✓

CONFIDENTIAL

MAKORCT-15

*A/P and Lateral Knee Radiographs collected post op ≤5 days after surgery are non-weight bearing

** MAKO CT Arthrogram to be performed if the patient has not had a previous MRI or MRI/CT Arthrogram. MAKO CT to be performed if the patient has had a previous MRI or MRI/CT Arthrogram.

Please refer to Section 11.0 Evaluations: Radiographs for the coverage specifications of each radiograph listed in the patient evaluation schedule.

2.0 INTRODUCTION

The number of Total Knee Replacement procedures is increasing due to an older demographic and a heavier population group. Individuals have higher expectations of their knee replacement surgery and function due to an increasing participation in sporting activities. As newer technologies are developing, the use of evidence based medicine is critically important (Walker et al. 2009).

The 2014 Australian National Joint Registry Annual Report states 41 250 patients underwent Unicompartamental Knee Replacement (UKR), 165 patients underwent Bicompartamental Knee Replacement (BKR) and 396 472 patients underwent Total Knee Replacement (TKR), with TKR figures increasing by more than 44 500 procedures from the previous 2013 report (AOANJRR).

In 2011 the Triathlon Total Knee System was the third most implanted prosthesis in England and Wales. In Australia it has been the most implanted prosthesis for Primary Total Knee Replacement since 2009 as reported by the National Joint Registry. Five year results report good midterm survivorship along with functional outcomes and patient satisfaction. (Scott et al. 2014)

Unicompartamental Knee Replacement and Patellofemoral replacement have both shown improved function and faster recovery times postoperatively. Interest in Bicompartamental

<http://sspintranet/sites/raqa/qms/documents/FM-CRD-029.docx>

MAKORCT-15 Final version 5.0 22 February 2018

CONFIDENTIAL

MAKORCT-15

Knee Replacement is increasing as innovation improves results, resulting in higher patient function levels (Argenson et al. 2009).

Currently there are a limited number of studies that report on Bicompartamental Knee Replacement outcomes, and even fewer prospective Randomised Control Trials (RCT) reported on this method. It has been idealised that Bicompartamental Knee Replacement may provide better function when compared to Total Knee Replacement, however additional studies are required (Engh et al. 2014).

Surgical accuracy in Total Knee Replacement has previously been improved by using computer assisted surgical navigation. New robotic arm technology has been developed to constrain the motion of the cutting tool used by the surgeon. The robotic arm remains under direct control of the surgeon, and the surgeon has the ability to dictate the movement constraints to increase reproducibility, accuracy and precision (Conditt et al. 2009)

Stryker's robotic arm assisted surgery offers treatment to patients who do not have osteoarthritis in all three compartments of the knee. A 3-D plan is created from the patients CT scan to provide implant size, placement and alignment. The robotic arm is controlled by the surgeon, and benefits of this technology include a smaller incision, live feedback, bone sparing capabilities and a shorter length of stay in hospital (Makoplasty)

This study will assess Bicompartamental Knee Replacement using Restoris MCK Multicompartamental Knee System, to Total Knee Replacement using Stryker's Primary Triathlon Total Knee System. Both surgeries will be conducted using Stryker robotic arm assisted surgery system (MAKO). Clinical and functional outcomes will be assessed between the two groups using the Oxford Knee Score as the primary endpoint. Radiographic outcomes will be collected to measure pre-operative cartilage wear, and any incidences of loosening and revision.

As all components used in this study are TGA approved, this will be a phase IV, post-market study.

<http://ssp.intranet/sites/raqa/qms/documents/FM-CRD-029.docx>

MAKORCT-15 Final version 5.0 22 February 2018

3.0 OBJECTIVES

PRIMARY

The primary objective of this study is:

- To compare the clinical outcomes of Knee Replacement surgery using the Oxford Knee Score (OKS) at 24 months, in patients receiving Bicompartamental Knee Replacement using Restoris MCK Multicompartmental Knee System with Stryker's robotic-arm assisted surgery system Mako, to Total Knee Replacement using the Triathlon Total Knee System performed with Stryker's robotic-arm assisted surgery system Mako.

SECONDARY

The secondary objectives of this study are:

- To determine functional and clinical outcomes of Bicompartamental Knee Replacement (BKR) and Total Knee Replacement (TKR) (including pain, function and health-related quality of life) with Restoris MCK Multicompartmental Knee System and Triathlon Primary Total Knee System at 24 months via:
 - EQ-5D: The EQ-5D is a standardised instrument for use as a measure of health outcome.
 - VAS Pain: A graphical Visual Analog Scale that patients use to indicate their level of pain.
 - New Knee Society Score 2011 (KSS): A validated score assessing surgeon generated objective measures based on technical outcomes, and subjective measures based on patient satisfaction, patient expectations and functional activity of the knee (Noble et al. 2012) (Scuderi et al. 2012).
 - Forgotten Joint Score (FJS): The Forgotten Joint Score is a newly-developed twelve-item, self-reported assessment of how aware recipients

of hip and knee joint replacement are of their joint in everyday life (Behrend et al, 2011).

- To compare incidence of loosening, reoperation and revision in patients receiving Restoris MCK Multicompartmental Knee System, compared to Triathlon Total Knee System.
- To determine length of hospital stay in patients receiving Restoris MCK Multicompartmental Knee System, compared to Triathlon Total Knee System.

4.0 NUMBER OF PATIENTS

This study will enrol a total of **70 cases**, of which 35 will be randomised to receive the Restoris MCK Multicompartmental Knee System and 35 will be randomised to receive the Triathlon Primary Total Knee System. See section 12.2 for sample size justification.

Additional patients will be recruited to compensate for early withdrawals and terminations.

5.0 LENGTH OF STUDY

Individual study patients will be followed up for a period of 2 years after surgery.

The enrolment period is expected to be 6-9 months or until the required sample size is reached; it is therefore anticipated that the entire study will take a further 33 months (minimum) to complete.

6.0 PATIENT SELECTION CRITERIA

The Investigator is responsible for evaluating each patient against the following criteria and assuring that the patient meets the requirements to be enrolled in this clinical investigation. Each patient enrolled in this investigation must meet each of the following inclusion criteria and have none of the exclusion criteria. The Investigator must notify the Ethics Committee of any patient enrolled in this study who does not meet the inclusion

and exclusion criteria. Inclusion/Exclusion criteria have been limited to reflect the actual patient population for this post-market assessment.

Investigators are also expected to follow the instructions for use of all devices involved in this study, in accordance with their usual clinical practice.

6.1 Inclusion Criteria

1. The patient is a suitable candidate for a Bicompartamental Knee Replacement and has moderate to severe patellofemoral wear and medial compartment wear (surgeons discretion)
2. The patient has no fixed flexion greater than 10 degrees.
3. The patient has maximal flexion greater than 100 degrees
4. The patient has a passively correctable varus deformity
5. The patient has a functionally Intact ACL.
6. The patient has no significant patellofemoral malalignment
7. The patient has negligible lateral compartment degeneration with no appreciable loss of cartilage height (surgeon's discretion).
8. The patient has pain that is not localised to the medial compartment only
9. The patient is a male or non-pregnant female.
10. The patient has signed the study specific, HREC-approved, Informed Consent document and is willing and able to comply with the specified pre-operative and post-operative clinical and radiographic evaluations.

6.2 Exclusion Criteria

1. The patient has a clinically deficient ACL and cruciate and collateral ligament insufficiency on MRI or MRI/CT Arthrogram.
2. The patient is undergoing revision surgery
3. The patient has greater than 10° of hyperextension, greater than 10° of varus or valgus deformity, greater than 10° Flexion Contracture
4. The patient has active, local infection or previous intra-articular infection
5. The patient has skeletal immaturity
6. The patient is without sufficient bone stock to allow appropriate insertion and fixation of the prosthesis

<http://ssp.intranet/sites/raqa/qms/documents/FM-CRD-029.docx>

MAKORCT-15 Final version 5.0 22 February 2018

7. The patient's weight, age or activity level might cause extreme loads and early failure of the system (surgeons discretion).
8. The patient has a systemic or local condition that would limit the ability to assess the performance of the device e.g. neuromuscular or neurosensory deficiency, disorder leading to progressive bone deterioration (including rheumatoid arthritis and osteoporosis), or patient is immunologically suppressed.
9. Patient has a cognitive impairment, an intellectual disability or a mental illness that is considered by the investigator to inhibit the patient's capacity to consent to research and the ability to participate in it
10. Patients with tricompartmental disease are contraindicated from the study

7.0 STUDY DESIGN

This is a prospective, randomised, study with patients treated at multiple hospitals.

Prior to each surgeon enrolling their first study patient, they must be accredited to perform Stryker's Robotic-arm Assisted Surgery. Accreditation includes attending a Surgical Skills training course provided by Stryker and led by a surgeon experienced with using Mako, review of the planning and surgical technique guides, surgical observation and consultation with current Mako users.

All potential study patients will be assigned a MAKORCT-15 study ID.

If a patient has previously had a MAKO CT Arthrogram and wishes to participate in the study, the patient is required to sign the study approved consent form and the previous MAKO CT Arthrogram will be used for study purposes.

If the patient has previously had a MRI or MRI/CT Arthrogram (within 6 months of planned study surgery date), the patient is required to sign the study approved consent form and the previous MRI or MRI/CT Arthrogram will be used for study purposes. Once the study consent form is signed, the patient will be referred for a MAKO CT for surgical planning purposes.

If a patient has not had a MAKO CT Arthrogram, MRI or MRI/CT Arthrogram and wishes to participate in the study, the patient is required to sign the study approved consent form, and once signed the patient will be referred for a MAKO CT Arthrogram.

<http://ssp.intranet/sites/raqa/qms/documents/FM-CRD-029.docx>

MAKORCT-15 Final version 5.0 22 February 2018

If the patient meets the Inclusion and Exclusion criteria and has signed the study consent form, the patient will be enrolled onto the study. If the patient does not meet the Inclusion and Exclusion criteria and has signed the study consent form, the patient will be terminated from the study as a Screen Failure.

Enrolled patients will be randomised to one of two equally sized groups either; the Restoris® MCK Multicompartmental Knee System group or the Triathlon Primary Total Knee System group. Randomisation will take place via the Investigator or designee using the central randomisation system within Inform for allocation to either group. Block randomisation will be performed by a statistician using specialised randomisation software with a block size of 4.

Any deviation from the assigned treatment will be reported as a deviation from Protocol.

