12.0 STATISTICAL METHODS

12.1 Enrolment and Randomisation

At least **35** patients per study group will be enrolled. Enrolment is defined as meeting the study Inclusion and Exclusion criteria.

<http://sspintraneet/sites/raqa/qms/documents/FM-CRD-029.docx>

MAKORCT-15 Final version 5.0 22 February 2018

The randomisation procedure by which the Knee System for the individual operation will be chosen (**Restoris® MCK Multicompartmental Knee System** versus the **Triathlon Primary Total Knee System**) will be centrally organised for all investigators, and allocated via block randomisation. At the time the patient meets the Inclusion and Exclusion criteria to take part in the study, the surgeon or designee will use the central randomisation system (via Inform) to obtain a randomised allocation. The block randomisation scheme will be performed using randomisation software with a block size of **4**. The randomisation scheme will ensure that during the enrolment period the ratio of the number of cases in the two groups remains approximately constant and that surgical kits are available for each case.

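### A fixed block size of 4 is printed in an open-label protocol and the level of blocking is not stated: up to one third of allocations could be foreseen if blocks run within hospital or surgeon, few or none on one central list

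*Combined protocol and SAP*

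**What the plan says.** The block size appears twice, as one constant: in Section 7.0 ("Block randomisation will be performed by a statistician using specialised randomisation software with a block size of 4") and in Section 12.1 ("The block randomisation scheme will be performed using randomisation software with a block size of" 4). Section 7.0 also says: "This is a prospective, randomised, study with patients treated at multiple hospitals". The numbers of hospitals and surgeons are not given.

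Section 12.1 describes the procedure as "centrally organised for all investigators, and allocated via block randomisation". Its aim is that "the ratio of the number of cases in the two groups remains approximately constant" and that surgical kits are available. No stratification factor is named in either section, and balance within hospital or surgeon is not mentioned.

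Section 12.1 fixes when the allocation is requested: "At the time the patient meets the Inclusion and Exclusion criteria to take part in the study". It also names who makes the request: "the surgeon or designee will use the central randomisation system (via Inform) to obtain a randomised allocation". Inclusion criteria 1 and 7 (Section 6.1) and exclusion criterion 7 (Section 6.2) are left to the surgeon's discretion. Under Section 7.0, consent and referral for any study CT come first. If a consented patient then fails the criteria, "the patient will be terminated from the study as a Screen Failure".

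**The concern.** Central allocation hides the list. It does not hide what a reader can deduce from a printed block size and a memory of past allocations. The surgeon implants the assigned device and no blinding is described, so each surgeon knows how his or her own earlier patients were allocated. The exposed step is the discretionary eligibility judgement immediately before the allocation is requested. Consent is not the exposed step, because it comes earlier.

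A recruiter who can foresee the next assignment could, deliberately or not, judge a borderline patient differently according to which implant is due. The two groups would then differ in ways randomisation was meant to prevent. How far this is possible depends on the level of blocking, which the plan leaves out.

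**Working it through.** **Inputs from the documents.** Block size 4 (Sections 7.0 and 12.1); 1:1 allocation (7.0); 70 patients (4.0, 12.2); SD 8.0, difference 6.0, two-sided 0.05, 29 per arm for 80% power (12.2). The plan gives no predictability figure to reproduce. Its sample size does reproduce: a two-sample t-test with 29 per arm has power 80.1%, and 29 × 1.2 = 34.8, rounded up to 35. The 29 and the SD are used below only for a standard error.

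**Assumed, because the documents do not say.** The number of strata, each recruiter's share of patients, and what each recruiter knows.

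**1. Blocks within hospital or surgeon, all earlier allocations in the stratum known.** A 1:1 block of 4 has 6 equally likely orders. An allocation is certain once one arm has filled its 2 places.

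| Place in block | Certain | Best guess right |
|---|---|---|
| 1 | 0 | 1/2 |
| 2 | 0 | 2/3 |
| 3 | 1/3 | 2/3 |
| 4 | 1 | 1 |

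Certain: (0 + 0 + 1/3 + 1)/4 = 1/3. Best guess: (1/2 + 2/3 + 2/3 + 1)/4 = 17/24 = 70.8%.

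These are ceilings, because last blocks may be incomplete. With 70 patients in equal strata:

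- 2 strata of 35: each has 8 full blocks plus 3 places, so 8 × 4/3 + 1/3 = 11 certain; 22/70 = 31.4%.
- 5 strata of 14: 3 full blocks plus 2 places, so 4 certain each; 20/70 = 28.6%.
- 10 strata of 7: 1 full block plus 3 places, so 5/3 certain each; 16.7/70 = 23.8%.

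**2. One central list, recruiter sees only his or her own cases.** Simulated lists of 70, optimal guess given the recruiter's own history:

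| Recruiter's share | Fixed 4 | Random 4/6 |
|---|---|---|
| 25% | 55.0% | 54.6% |
| 33% | 56.4% | 55.7% |
| 50% | 58.7% | 57.7% |
| 90% | 67.3% | 65.3% |

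No allocation was certain in any row. The simulation assumes the recruiter cannot tell how many other patients were randomised in between. A recruiter who can tell has more information, and some allocations can then become certain.

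**3. Effect of randomly varying sizes 4 and 6 within hospital or surgeon.** The guesser is assumed to know that sizes are 4 or 6, but not their order. For lists of 12 to 70, certain allocations fall from about one third to 5.6% to 6.4%, and the best guess from 70.8% to between 68.0% and 69.1%. So the change removes most of the certainty but little of the guessing advantage. On one list the guess rate falls by 0.4 to 1.0 points for shares of 25% to 50%.

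**4. Scale in Oxford Knee Score points (illustration only).** Let the gap be the assumed difference in expected 24-month score between patients entered when one implant is expected and those entered when the other is. If every enrolment is steered and none of the gap runs through the baseline score, bias = gap × (2 × guess rate − 1). For a gap of 2:

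- Within hospital or surgeon: 2 × (2 × 17/24 − 1) = 0.83.
- One list, shares 25% to 50%: 2 × (2 × 0.550 − 1) = 0.20 to 2 × (2 × 0.587 − 1) = 0.35.

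The standard error of the planned comparison is 8 × √(2/29) = 2.10. With within-hospital blocks, steering half of enrolments, or having half of the gap run through the baseline score (a model covariate under Section 12.4), reduces the 0.8 to about 0.4. None of the gap or steering inputs comes from the documents.

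**The case against.** The best case for the plan is that its plain reading is one unstratified list. Section 12.1 describes a procedure organised centrally for all investigators, its balance aim is overall, no stratification factor is named, and the model in Section 12.4 has no site term. On that reading nothing is certain to a recruiter who sees only his or her own cases, and varying the sizes gains about 1 point of guess rate or less. A statistician generates the scheme and a central system releases allocations. Screen failures are recorded, consenting patients are logged (Section 15.0) and monitors verify source data (Section 16.0), so selective refusal would leave a trace. A small block also serves the stated aims of a near-constant ratio and available kits.

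Most of this stands, and it limits the weight of the point. It does not close it. A central system can hold a separate list for each hospital, so the level remains open. A trace of refusals does not prevent them. Blocks of 4 and 6 keep the balance aim almost intact. Nothing in the plan needs the size to be printed where investigators can read it.

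A reader might infer three stronger things that the documents do not support:

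- That one third of allocations in this trial are known in advance. This needs blocking within hospital or surgeon, complete blocks, and knowledge of every earlier allocation in the stratum, including colleagues' cases if blocks run by hospital.
- That the treatment effect is biased by about 0.8 points. That figure rests on an assumed gap and on every enrolment being steered; nothing in the documents shows that any steering takes place.
- That the model must contain a site term. This follows only if blocking is in fact by site or surgeon.

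**Conclusion.** The point holds as a design weakness worth correcting, at modest weight. In an open-label trial with discretionary entry criteria, printing one small constant block size gives away information for no benefit. The consequence depends on a fact the plan omits. Under blocking within hospital or surgeon, and with full knowledge of the stratum, the ceiling of one third certain and 71% guessable applies. Under one list, which the text favours, a recruiter with a quarter to a half of patients has only a slight advantage over chance. That advantage grows if one recruiter enters most patients or can tell how many others were randomised in between. The block calculations are exact; the one-list and 4/6 figures are simulated under the stated assumptions. No bias in score points can be derived from the documents. The sample size is not affected.

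**What to change.** For patients not yet randomised, regenerate the list with randomly varying block sizes, for example 4 and 6, at whatever level of blocking is already in use. Delete the size from Sections 7.0 and 12.1 and hold it in a restricted randomisation document. In the same edit, state whether blocks run across the trial, by hospital or by surgeon. Do not move a single central list to within-hospital blocks for this purpose, since that would make allocations easier to foresee.

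Leave the repeated-measures model as it is if there is one list. Only if blocking is by hospital or surgeon should that factor be added, as a random intercept or with small sites pooled by a rule fixed in advance.

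The costs are a regenerated list, slightly looser balance (largest imbalance within a block 3 instead of 2), and written Ethics Committee approval of the wording change, which Section 18.0 requires. If all patients have already been randomised, only the statement of the level remains to be made.
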